16.3 Appendix 3: Yamaguchi criteria

Major criteria

- Fever $\geq 39^{\circ}\text{C}$ lasting 1 week or more
- Arthralgia lasting 2 weeks or more
- Typical skin rash: maculopapular, nonpruritic, salmon-pink rash with concomitant fever spikes
- Leukocytosis $\geq 10,000/\text{mm}^3$ with neutrophil polymorphonuclear proportion $\geq 80\%$

Minor criteria

- Pharyngitis or sore throat
- Lymphadenopathy and/or splenomegaly
- Liver enzyme abnormalities (aminotransferases)
- Negative for RF or antinuclear antibodies

Exclusion criteria

- Infection, especially sepsis and Epstein–Barr viral infection
- Malignant diseases, especially lymphomas
- Inflammatory disease, especially polyarteritis nodosa

Classification requirement

- At least five criteria, including two major criteria and no exclusion criteria

**Document History – Changes compared to previous final version of SAP**

CCI

CCI

CCI

## List of abbreviations

AE	Adverse Event
CRF	Case Report Form
CSR	Clinical Study Report
DMS	Document Management System
FAS	Full Analysis Set
IA	Interim Analyses
LLN	Lower Limit of Normal
LLQ	Lower Limit of Quantification
MedDRA	Medical Dictionary for Drug Regulatory Affairs
OMU	Original Measurement Unit
PK	Pharmacokinetics
CCI	
RAP	Reporting & Analysis Process
SAP	Statistical Analysis Plan
SAS	Statistical Analysis System
SMQ	Standardized MedDRA Queries
TFLs	Tables, Figures, Listings
ULN	Upper Limit of Normal
ULQ	Upper Limit of Quantification
WHO	World Health Organization

## 1 Introduction

The purpose of this Statistical Analysis Plan (SAP) is to describe the implementation of statistical analyses planned in the study protocol, and to provide detailed statistical methods that will be used for the Clinical Study Report (CSR) of study CACZ885G1302.

Data will be analyzed according to the data analysis Section 12 of the study protocol which will be available in Appendix 16.1.1 of the CSR. Important information is given in the following sections and additional details will be provided, as applicable, in Appendix 16.1.9 of the CSR.

This SAP covers statistical and analytical plans for the primary efficacy analysis based on the data up to the time when the first 11 participants have reached Week 28 (or prematurely discontinued prior to Week 28), a 28 Week interim analysis after all participants have completed Week 28, a 48 Week interim analysis after all participants have completed Week 48 and the final analysis after all participants have completed the study.

The following documents were referenced while writing this SAP:

- Study protocol: Clinical Trial Protocol CACZ885G1302 version 03 dated 19-May-2023
- Case Report Forms:
  - CACZ885G1302\_Unique Blank eCRF Layout\_Version 4.0
  - CACZ885G1302\_Expanded Blank eCRF Layout\_Version 4.0
  - CACZ885G1302\_Annotated eCRF layout\_Version 4.0

### 1.1 Study design

This study is an open-label, single-arm active treatment study to evaluate efficacy, safety, tolerability and PK/PD of canakinumab 4 mg/kg (maximum of 300 mg) every four weeks subcutaneously administered for at least 48 weeks in Japanese participants with AOSD until canakinumab is approved and commercially available for AOSD in Japan or Novartis terminates the study. Approximately 21 participants will be enrolled in the study.

[figure not shown]
The study will consist of two distinct study epochs as outlined below (see also [Figure 1-1](#)):

- Screening epoch: Day -28 to Day -1
- Open label treatment epoch: Day 1 to approval and commercially available or study termination, whichever comes first.

Two interim analyses will be performed for this study - first IA after all participants have completed Week 28 to support the registration dossier, and second IA at Week 48 to supplement the dossier with long-term safety and efficacy data. At the interim analysis at Week 28, the primary efficacy analysis will be conducted based on the data up to the time when the first 11 participants have reached Week 28 (or prematurely discontinued prior to Week 28), CCI

Final analysis will be performed after all participants have completed the study.

**Figure 1-1 Study design**

The primary efficacy analysis using the data up to the time when the first 11 participants have reached Week 28 (or prematurely discontinued prior to Week 28) will be performed at Week 28 interim analysis.

## 1.2 Study objectives and endpoints

**Table 1-1 Objectives and related endpoints**

Objective(s)	Endpoint(s)
Primary objective(s)	Endpoint(s) for primary objective(s)

To evaluate the efficacy of canakinumab with respect to the adapted ACR 30 response after 8 weeks treatment

	

Proportion of participants who achieve adapted ACR 30 response at Week 8

Secondary objective(s)	Endpoint(s) for secondary objective(s)

To evaluate ability of canakinumab to taper corticosteroids based on success criteria starting from Week 8 to Week 28

To evaluate the efficacy of canakinumab with respect to the adapted ACR 30/50/70/90/100 response over time

To evaluate the efficacy of canakinumab on the systemic feature score over time

To evaluate the efficacy of canakinumab with respect to the components of adapted ACR criteria over time

To evaluate ability of canakinumab to taper corticosteroids dose over time after Week 8

To evaluate the efficacy of canakinumab on rash over time

To evaluate the efficacy of canakinumab on DAS28-CRP

To assess the safety and tolerability of canakinumab

	

Proportion of participants who are able to taper corticosteroids based on success criteria at Week 28.

Proportion of participants who achieved adapted ACR 30/50/70/90/100 response criteria at Day 15 and all subsequent visits.

Change from baseline in Systemic Feature Score (total score and each components) at Day 15 and all subsequent visits.

Change from baseline in each component of adapted ACR at Day 15 and all subsequent visits

Change from baseline of corticosteroid dose at all visits after Week 8.

Presence of rash (typical/atypical) at all visits during study.

Change from baseline in DAS28-CRP at Day 15 and all subsequent visits.

Incidence and severity of Treatment Emergent AEs. Proportion of participants up to end of study with:

Objective(s)	Endpoint(s)
	

- Adverse events

- Serious adverse events

- AEs related to study drug

- AEs leading to discontinuation



• To evaluate the pharmacokinetics (PK) / pharmacodynamic (PD) of canakinumab

	

• Means and mean change over time of:

-Vital sign parameters

-Laboratory parameters

• Canakinumab concentrations over time

• Total IL-1<math>\beta</math> (sum of IL-1<math>\beta</math> free and bound to canakinumab) level s over time

• To assess the immunogenicity of canakinumab

	

• Anti-canakinumab antibody identification and titer at BSL, Week 24, Week 48 and every 24 weeks until EOS.

Exploratory objective(s)	Endpoint(s) for exploratory objective(s)

Successful oral corticosteroids tapering is defined as meeting one of the following in terms of prednisone equivalent dose per day (mg/kg/day).

- Participants with prednisone equivalent dose of  $> 0.8$  mg/kg/day at baseline were able to reduce their dose to  $\leq 0.5$  mg/kg/day.
- Participants with prednisone equivalent dose from  $\geq 0.5$  mg/kg/day and  $\leq 0.8$  mg/kg/day at baseline were able to reduce their dose by at least 0.3 mg/kg/day.
- Participants with any initial prednisone equivalent dose at baseline were able to reduce their dose to  $\leq 0.2$  mg/kg/day.
- Participants with prednisone equivalent dose of  $\leq 0.2$  mg/kg/day at baseline were able to reduce their dose with any reduction.

AND maintaining a minimum adapted ACR30 response.

Details on how to calculate the prednisone equivalent dose per day are given in [Section 5.6.1](#).

Unless otherwise stated, the terms “prednisone equivalent dose” means prednisone equivalent dose of oral steroids.

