4.1 Rationale for study design

Study G1302 is an open-label, single-arm study in Japanese AOSD patients to evaluate the efficacy and safety of canakinumab 4 mg/kg (maximum 300 mg) subcutaneously administered every 4 weeks. Conducting a large-scale confirmatory trial is not feasible because the number of AOSD patients who can be enrolled in this study is limited. Regarding the rationale for an open-label study, placebo administration to AOSD participants who do not respond to corticosteroids has a safety risk of worsening the underlying disease leading to macrophage activation syndrome (MAS), a serious complication that can be fatal. Since tocilizumab is available as an approved treatment option in Japan, conducting a placebo-controlled study for AOSD participants who do not respond to corticosteroids would not be enrolled. In addition, SOC control arm of tocilizumab is not feasible, since controlled trial with tocilizumab failed and G1302 study allows participants previously treated with tocilizumab who have discontinued treatment due to safety or efficacy issues to enter study.

To compare the efficacy for Japanese AOSD and previously-treated SJIA participants, assessment time points for primary and key secondary endpoint are consistent with those evaluated in the SJIA study. Adapted ACR 30 will be assessed at Week 8 as primary endpoint. If improvements in disease activity are observed after Week 8, tapering of corticosteroid dose will be started, and the proportion of participants who have successfully reduced corticosteroid dose at Week 28 will be assessed as a key secondary endpoint.

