6. With underlying metabolic, renal, hepatic, infectious or gastrointestinal conditions which in the opinion of the investigator compromises the participant and/ or places the participant at unacceptable risk for participation in an immunomodulatory therapy.
7. Clinical evidence of liver disease or liver injury as indicated by abnormal liver function tests at screening such as Aspartate Aminotransferase (AST), Alanine Aminotransferase (ALT), Gamma-glutamyl transferase (GGT), alkaline phosphatase (ALP)(must not exceed 3 times the upper limit value of the normal range for age), or serum bilirubin (must not exceed twice the upper limit value of the normal range for age). Exception: participants who exceed this limit after initiating latent TB treatment may be eligible for participation in this study pending confirmation with Novartis.
8. Presence of moderate to severe impaired renal function as indicated by clinically significantly abnormal creatinine ($\geq 1.5 \times$ upper normal limit ULN) or abnormal urinary constituents (e.g., albuminuria) at screening. Evidence of urinary obstruction or difficulty in voiding at screening.
9. Use of concomitant treatments including disease-modifying and/or immunosuppressive drugs with the exception of:
 - Stable daily dose of systemic corticosteroid treatment ≥ 10 mg AND ≤ 1.0 mg/kg/day (maximum 60 mg/day) of oral prednisone (or equivalent) for at least 1 week prior to baseline
 - Stable dose of no more than one non-steroidal anti-inflammatory drug (NSAID) for at least 1 week prior to the baseline visit
 - Stable dose of methotrexate (maximum of 20 mg/m²/week) for at least 4 weeks prior to the baseline visit, and folic/folinic acid supplementation (according to standard medical practice of the center)
10. Use of following therapies:
 - Anakinra within 24 hours prior to baseline visit
 - Rilonacept within 1 week prior to baseline visit
 - Tocilizumab within 3 weeks prior baseline
 - Etanercept within 4 weeks prior baseline
 - Infliximab within 12 weeks prior to the baseline visit
 - Golimumab within 12 weeks prior to the baseline visit
 - Adalimumab within 8 weeks prior to the baseline visit
 - Abatacept within 10 weeks prior to the baseline visit
 - Rituximab within 26 weeks prior to the baseline visit

- Leflunomide within 4 weeks prior to the baseline visit. Documentation of a completion of a full cholestyramine elimination treatment after most recent leflunomide use will be required.

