8.3.2 Corticosteroid tapering

Participants using concomitant corticosteroids at study entry may begin to reduce their corticosteroid dose to the lowest possible dose/discontinuation beginning at Week 8 until the End of Study as detailed in [Section 6.2.1.1](#) of the protocol.

Successful oral corticosteroid tapering is defined as meeting one of the following:

- Participants with prednisone equivalent dose of > 0.8 mg/kg/day at baseline were able to reduce their dose to ≤ 0.5 mg/kg/day.
- Participants with prednisone equivalent dose from ≥ 0.5 mg/kg/day and ≤ 0.8 mg/kg/day at baseline were able to reduce their dose by at least 0.3 mg/kg/day.
- Participants with any initial prednisone equivalent dose at baseline were able to reduce their dose to ≤ 0.2 mg/kg/day.
- Participants with prednisone equivalent dose of ≤ 0.2 mg/kg/day at baseline were able to reduce their dose with any reduction

AND maintaining a minimum adapted ACR30 response.

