## **2.6.2 Statistical hypothesis, model, and method of analysis**

Frequency table with the number and percentage of participants who were able to taper oral corticosteroids successfully at Week 28 will be provided for the participants in the FAS who used systemic corticosteroid at baseline and were administered study treatment at Week 8, i.e. the number of evaluable participants could be smaller than the number of participants in the FAS. Participants who were able to taper oral corticosteroids successfully at Week 28 will be classified as “Tapered” or “Steroid free”, and “Steroid free” is defined as participants that did not use the steroid in the last point of time.

This analysis will also be performed by the subgroups described in Section 2.2.1.

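### The key secondary tapering definition does not ensure that a counted success took a lower steroid dose, and the rate is planned without an interval

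*SAP*

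**What the plan says.** SAP 1.2 (below Table 1-1) combines four routes by a logical OR: "Successful oral corticosteroids tapering is defined as meeting one of the following". Protocol 8.3.2 lists the same four. In prednisone-equivalent mg/kg/day they are:

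- Route 1: baseline above 0.8, Week 28 at or below 0.5.
- Route 2: baseline 0.5 to 0.8, fall of at least 0.3.
- Route 3: "Participants with any initial prednisone equivalent dose at baseline were able to reduce their dose to" 0.2 or less.
- Route 4: baseline at or below 0.2; participants "at baseline were able to reduce their dose with any reduction".

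A further condition applies throughout: "AND maintaining a minimum adapted ACR30 response".

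SAP 5.6.1 sets the dose calculation. Baseline mg/kg uses the Day 1 weight, or the last one before it. Post-baseline mg/kg uses the latest weight on or before the dose date. No rule says how a reduction is to be coded, and no tolerance or rounding is given.

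SAP 2.6.2 plans only this summary: "Frequency table with the number and percentage of participants who were able to taper oral corticosteroids successfully at Week 28". The primary endpoint, by contrast, has a 95% confidence interval (SAP 2.5.2). Protocol 4.1 explains that the timing of the primary and key secondary endpoints follows the SJIA study: "To compare the efficacy for Japanese AOSD and previously-treated SJIA participants".

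**The concern.** A tapering endpoint should count only people whose steroid dose went down. Two features of the definition leave that open.

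First, route 3 takes any starting dose, so it also covers the participants for whom route 4 was written. Route 4 then has no work of its own. That invites a programmer to treat route 3 as a simple test of the Week 28 dose against 0.2, which drops the requirement of a reduction for low-dose starters.

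Second, the comparison is made in mg/kg/day with a different weight at each end. Weight gain alone can produce a reduction.

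No other rule catches these cases. The primary estimand makes any systemic steroid increase before Week 8 a non-response. The secondary estimand (Protocol 2.2, SAP 2.6.1) fails only intravenous use, while Protocol 6.2.1.1 foresees a return to the prior oral dose or higher if disease worsens. SAP 2.14 also reports tapering success by visit, so a misclassification could recur across visits.

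At stake is a percentage on at most 11 or 14 people, shown without an interval.

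**Working it through.** The documents state no expected tapering rate or interval for this endpoint, so there is no planned figure to reproduce.

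**Can participants start at or below 0.2 mg/kg/day?** The entry rule (Protocol 5.2, the exception beginning "Stable daily dose of systemic corticosteroid treatment") sets a floor of 10 mg/day. 10 mg / 0.2 mg/kg = 50 kg, so anyone of 50 kg or more on 10 mg/day is in the band. At 60 kg, 10/60 = 0.167; at 75 kg, 10/75 = 0.133. SAP 2.3.2 already lists a baseline category from above 0 to 0.2.

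**Do routes 3 and 4 do different work?** Take baseline b from 0.01 to 1.00 and Week 28 dose p from 0 to 1.00, in steps of 0.01, and code route 3 in three ways:

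| Route 3 coding | Condition |
|---|---|
| Literal | p ≤ 0.2 and p < b |
| Threshold only | p ≤ 0.2 |
| Limited | p ≤ 0.2 and b > 0.2 |

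- Route 4 (b ≤ 0.2 and p < b) adds no pair beyond route 3 under the literal or the threshold coding.
- Literal and threshold coding differ in 210 pairs, all with b ≤ 0.2 and b ≤ p ≤ 0.2. The count checks by hand: 20 + 19 + … + 1 = 20 × 21 / 2 = 210.
- Literal and limited coding differ in no pair.

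Example at a constant 60 kg, baseline 10 mg/day (0.1667): staying at 10 mg, or rising to 12 mg (12/60 = 0.200), passes under threshold coding and fails under the other two.

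**Does weight alone create a reduction?** Hold the dose at 10 mg/day and apply SAP 5.6.1:

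| Weight, baseline to Week 28 | Baseline mg/kg/day | Week 28 mg/kg/day | Result on the literal reading |
|---|---|---|---|
| 60 to 61 kg | 10/60 = 0.1667 | 10/61 = 0.1639 | Success (routes 3 and 4) |
| 60 to 59 kg | 10/60 = 0.1667 | 10/59 = 0.1695 | Failure |
| 49 to 50 kg | 10/49 = 0.2041 | 10/50 = 0.2000 | Success (route 3) |

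The first case passes under all three codings. The third starts just above 0.2, so limiting route 3 does not remove it either. Weight is recorded to 0.1 kg (Protocol 8.4), and 10/60.1 = 0.1664 is already below 0.1667. Every success above still requires ACR30 to be held.

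**Size.** One misclassified participant shifts the rate by 1/11 = 9.1 points or 1/14 = 7.1 points; two shift it by 18.2 or 14.3. SAP 2.6.2 notes that the denominator may be smaller than the FAS. With 9 evaluable (an assumption), one participant is 11.1 points.

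**Interval.** Clopper-Pearson limits are the 2.5% quantile of Beta(x, n − x + 1) and the 97.5% quantile of Beta(x + 1, n − x). The counts are illustrative:

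| x/n | Rate | Exact 95% CI |
|---|---|---|
| 6/11 | 54.5% | 23.4 to 83.3 |
| 8/11 | 72.7% | 39.0 to 94.0 |
| 7/14 | 50.0% | 23.0 to 77.0 |
| 10/14 | 71.4% | 41.9 to 91.6 |

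**The case against.** The strongest reply is that route 3 speaks of reducing the dose, so an unchanged or raised dose fails as written. Redundancy in an OR list misclassifies nobody, and route 4 states the intent for low-dose starters. SAP 2.6.2 labels successes as tapered or steroid free, and SAP 2.7.2 summarises change in oral dose in mg/day by visit, so with 11 to 14 participants an anomaly might be noticed. The affected band is also narrow: 10 to 12 mg/day at 60 kg.

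Much of this stands. A reader might infer that the plan itself counts an unchanged or higher mg/kg dose as tapered. The documents do not support that: it follows only if the program ignores the verb, and no section says that it will. But the reply does not reach the weight effect, which arises on the literal reading. Nor does a group summary in mg/day change an individual's classification.

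On the interval, the endpoint is descriptive, and n/N lets a reader compute one. A reader might also infer that a formal comparison of tapering rates with the SJIA study is planned. Protocol 4.1 only aligns assessment times for comparison, and no such test is specified. The interval is therefore a modest addition for consistency with the primary endpoint, not the repair of a failed inference.

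**Conclusion.** The point holds in a limited form. Under the rules as written, a participant whose mg/day dose has not changed can be a key secondary success through weight gain alone, provided ACR30 is held. In addition, the overlap of routes 3 and 4 and the absence of a coding rule leave room for a threshold-only program that would also pass unchanged or higher doses in the low-dose band.

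The effect on the rate cannot be computed, because the documents give neither the number starting at or below 0.2 mg/kg/day nor the weight changes. It may be zero. The per-participant shift assumes that all 11 or 14 are evaluable. The point concerns how the endpoint is scored, not how steroids are tapered in the clinic.

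**What to change.** 1. In SAP 1.2 and 5.6.1, state that success in every route requires the Week 28 prednisone-equivalent daily dose in mg to be below the baseline daily dose in mg, in addition to the existing mg/kg/day criteria. This closes both the weight effect and the threshold-coding gap.
2. Limit route 3 to baseline above 0.2 mg/kg/day, so that route 4 alone governs those at or below it. This changes no classification under the literal reading.
3. In SAP 2.6.2, report the proportion with an exact (Clopper-Pearson) 95% confidence interval.

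The cost is a phrase or two in the definition and a slightly wider table. The mg/day dose is already derived for SAP 2.7.2. The reported success rate may come out slightly lower. A breakdown by baseline dose band is not needed: the cells would hold very few people, and SAP 2.1 rules out stratified analyses.

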## **2 Statistical methods**

### **2.1 Data analysis general information**

The statistical analysis will be performed by Novartis using SAS 9.4 TS Level 1M6 or above.

Summary statistics for continuous variables will generally include n, mean, standard deviation, median, minimum, and maximum. For categorical variables, this will generally include frequency and percentage. For selected parameters, 25th and 75th percentiles will also be presented when applicable.

The data cut-off date for Week 28/Week 48 IA will be the date of Week 28/Week 48 visit for the last participant. For efficacy analyses, the data up to Week 28/Week 48 visit for each individual participant will be included. For safety analyses and summaries for treatments, all available data will be included.

No center-specific or stratified analyses will be performed.

#### **2.1.1 General definitions**

##### **Study treatment**

Study treatment refers to subcutaneous injection of canakinumab (ACZ885).

##### **Date of first/last administration of study treatment**

Date of first/last administration of study treatment is the date that the participant is first/last administered study treatment.

##### **Study day**

For efficacy and safety assessments, study day will be calculated relative to Day 1, the first dose day.

If Date of assessment  $\geq$  Day 1 date,

$$\text{Study Day} = \text{Date of assessment} - \text{Day 1 date} + 1$$

If Date of assessment  $<$  Day 1 date,

$$\text{Study Day} = \text{Date of assessment} - \text{Day 1 date}$$

##### **Baseline**

Baseline is the last assessment (including screening visits and unscheduled visits) obtained before the first administration of the study treatment.

## On-treatment period

Treatment period is from the date of first administration of study treatment to the end of study (EOS) for each participant.

### 2.1.2 Analysis visit

In the analysis of each visit, analysis visit is required to specify the time point to be analyzed. The visit name as reported in the eCRF will be used except for the end of study (visit name = EOS), which will be mapped according to [Table 2-1](#).

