9.1 Discontinuation from study treatment and from study

9.1.1 Discontinuation from study treatment

Discontinuation of study treatment for a participant occurs when study treatment is permanently stopped for any reason (prior to the planned completion of study treatment administration, if any) and can be initiated by either the participant or the investigator.

The investigator must discontinue study treatment for a given participant if, he/she believes that continuation would negatively impact the participant's well-being.

Discontinuation from study treatment is required under the following circumstances:

- Participant/guardian decision
- Pregnancy
- Use of prohibited treatment as per recommendations in the prohibited treatment section
- Any situation in which continued study participation might result in a safety risk to the participant
- Any severe or serious adverse event that is not compatible with administration of study medication, including adverse events that require treatment with an unacceptable co-medication
- Onset of malignancy
- Occurrence of uncontrolled life-threatening infection
- Any other protocol deviation that results in a significant risk to the participant's safety

The investigator should consider discontinuing participants from study treatment who experience a clinically important worsening of disease activity compared to baseline at two consecutive visits after Week 4. A clinically important worsening will be defined as participants who do not meet the adapted ACR30 criteria by Week 12 or participants with non-response (defined as Adapted ACR <30) at two consecutive visits at any time in the study beginning at Week 12.

All participants who discontinue will complete an EOS visit, be discontinued from the trial and be treated as per standard local medical practice (see also [Section 10.1.3](#) for information on SAE reporting following the last dose of study medication).

If discontinuation from study treatment occurs, the investigator should make a reasonable effort to understand the primary reason for the participant's discontinuation from study treatment and record this information.

Participants who discontinue from study treatment agree to return for the end of treatment and follow-up visits indicated in the Assessment Schedule (refer to Section 8).

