**Table 2-1 Visit window**

Protocol defined			Time point to be analyzed	Visit window (days) for mapping end of study visit
Epoch	Week	Day		
Screening	-4	-28 to -1	Baseline	-28 to -1
Open-label treatment	1	1	Baseline	1
	1	3	Day 3	2-4
	2	15	Day 15	5-16
	4	29	Week 4	17-31
	8	57	Week 8	32-60
	12	85	Week 12	61-88
	16	113	Week 16	89-116
	20	141	Week 20	117-144
	24	169	Week 24	145-172
	28	197	Week 28	173-200
	32	225	Week 32	201-228
	36	253	Week 36	229-256
	40	281	Week 40	257-284
	44	309	Week 44	285-312
	48	337	Week 48	313-340
	Every 4 weeks after Week 48	X	Every 4 weeks after Week 48	(X-24) – (X+3)

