## **Discontinuation of study treatment before Week 8 for any reason**

Treatment policy strategy is applied to this intercurrent event. When a participant discontinued study treatment before Week 8, but adapted ACR 30 assessment at Week 8 is available, it will be included in the analysis.

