### **2.5.4 Handling of missing values/censoring/discontinuations**

Missing adapted ACR 30 assessment at Week 8 will be imputed with non-responder regardless of the reason for missing data (non-responder imputation).

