At the interim analyses, for participants who discontinued before Week 28/Week 48 visit, the data up to the time of discontinuation will be included for efficacy and safety analyses. For participants who discontinued after Week 28/Week 48 visit, all available data up to the time of discontinuation will be included for safety analyses, but the data up to Week 28/Week 48 will be included for efficacy analyses. For participants who early discontinued, the EOS visit will be remapped using the pre-defined time window before the data cut-off. When the data up to the specific timepoints cannot be extracted, all data available at data base lock will be reported.

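### For the primary endpoint, an end-of-study visit up to 25 days before Day 57 is analysed as Week 8, which bypasses the plan's non-responder imputation

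*SAP*

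**What the plan says.** SAP 2.1.2 takes the visit name from the eCRF "except for the end of study (visit name = EOS), which will be mapped according to" Table 2-1. The relevant column of that table is headed "Visit window (days) for mapping end of study visit". For Week 8 (Day 57) it gives Days 32-60, and for Week 28 (Day 197) Days 173-200. SAP 2.14 applies the mapping to leavers at the interim analyses: "For participants who early discontinued, the EOS visit will be remapped using the pre-defined time window before the data cut-off". The primary efficacy analysis is part of the Week 28 interim analysis.

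Two rules decide what a Week 8 value does in the primary analysis. Under SAP 2.5.3, if a participant has stopped treatment "but adapted ACR 30 assessment at Week 8 is available, it will be included in the analysis". Under SAP 2.5.4, "Missing adapted ACR 30 assessment at Week 8 will be imputed with non-responder regardless of the reason for missing data"; protocol 12.4.4 says the same.

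The assessment schedule (protocol Table 8-1) includes the adapted ACR assessment at EOS, so a leaver will normally have a value that can be mapped. Protocol 9.1.1 has everyone who discontinues complete an EOS visit and leave the trial. It then says: "Participants who discontinue from study treatment agree to return for the end of treatment and follow-up visits indicated in the Assessment Schedule".

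**The concern.** Someone whose last assessment is an EOS visit on Days 32-56 was never assessed at Week 8. Under the missing-data rule that person is a non-responder. The mapping supplies a value first, so the rule has nothing to act on. What enters the analysis is the participant's status at exit, at the earliest three days after the nominal Week 4 visit (Day 29), under a Week 8 label.

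There is a second effect. The composite strategy makes a steroid increase or intravenous steroid use before Week 8 a non-response. If the participant leaves the trial at an early EOS visit, increases after that day go unseen. For an EOS on Day 32, 31 days after Day 1 are observed instead of 56.

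At stake is the only hypothesis-tested endpoint, in 11 participants. Contiguous windows of this width may suit descriptive by-visit tables. They fit poorly with an endpoint that carries its own rule for a missing assessment.

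**Working it through.** **Inputs**
- Nominal days and EOS windows, SAP Table 2-1: Week 4, Day 29 (17-31); Week 8, Day 57 (32-60); Week 12, Day 85 (61-88); Week 28, Day 197 (173-200).
- n = 11 (SAP 2.5.1). Null rate 0.40, one-sided 2.5%, normal-approximation binomial test, Wald interval with continuity correction (SAP 2.5.2).
- The sample-size section is redacted and no dropout rate is given, so there is no planned figure to reproduce. The number of early EOS visits below is an assumption.

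**1. Width of the windows**
- Week 8: 57 − 32 = 25 days early; 60 − 57 = 3 days late.
- Week 28: 197 − 173 = 24 days early; 200 − 197 = 3 days late.

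**2. What happens to a leaver with no named Week 8 visit**

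| EOS on Day | Analysed as | Week 8 ACR 30 |
|---|---|---|
| 17-31 | Week 4 | missing, so non-response |
| 32-56 | Week 8 | the EOS value, response or not |
| 57-60 | Week 8 | the EOS value, response or not |
| 61-88 | Week 12 | missing, so non-response |

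An EOS visit 25 days early counts as Week 8; one four days late does not.

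**3. Weight of one participant**

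One of 11 is 1/11 = 9.1 percentage points. With x responders:
- uncorrected z = (x/11 − 0.40) / √(0.40 × 0.60 / 11), denominator 0.1477
- corrected z = (x − 0.5 − 4.4) / √(11 × 0.40 × 0.60), denominator 1.6248

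| x | z, one-sided p (uncorrected) | z, one-sided p (corrected) | Wald 95% interval, corrected |
|---|---|---|---|
| 7 | 1.600, 0.0548 | 1.292, 0.0981 | 0.307 to 0.966 |
| 8 | 2.216, 0.0134 | 1.908, 0.0282 | 0.419 to 1 |
| 9 | 2.831, 0.0023 | 2.523, 0.0058 | 0.545 to 1 |

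The deciding step is 7 to 8 without continuity correction and 8 to 9 with it. SAP 2.5.2 attaches the correction to the interval and does not say whether the test is corrected.

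**4. Chance of reaching 8 of 11 (illustration)**

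Assume each participant meets ACR 30 with probability p, at an early EOS visit as at Week 8, and that k participants leave with an EOS visit on Days 32-53. With the wide window all 11 can respond; if early EOS values are treated as missing, only 11 − k can.

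| p | wide window | k = 1 | k = 2 | k = 3 |
|---|---|---|---|---|
| 0.40 | 0.0293 | 0.0123 | 0.0038 | 0.0007 |
| 0.70 | 0.5696 | 0.3828 | 0.1960 | 0.0576 |

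The 0.0293 is what the uncorrected test gives at the null rate with no early leavers, so the window does not create it. The window removes the reduction that non-responder imputation would bring.

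**The case against.** The strongest reply is that the effect is hypothetical. It needs a participant among the 11 with an EOS visit before a true Week 8 visit, a met ACR 30 with no intermittent fever in the preceding week, no steroid increase or intravenous steroid, and a total exactly at the threshold. Nothing in the documents shows that this occurred, and a mapped value may equally be a non-response. All of that stands and limits the size of the point. It does not change what the rule does.

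It is also fair to say that early EOS visits may be uncommon. Protocol section 8, the glossary and part of 9.1.1 have participants who stop treatment continue with visits; in that case the named Week 8 visit is used. A reader might infer from 9.1.1 that leaving at EOS is the usual path, but that section contradicts itself, so the inference is not supported.

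The tolerance is a judgement. Named visits carry no date limit, so under a Days 54-60 rule a named Week 8 visit on Day 53 would count while an EOS visit on Day 53 would not. The table's +3 days is the edge of a bin, not a stated accuracy limit. This stands, and it is why a sensitivity analysis belongs with the fix.

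Two stronger readings are tempting:
- **Participants who stop for harm are wrongly made responders.** The primary estimand ignores treatment discontinuation for any reason, so someone who stopped for harm and meets ACR 30 at Week 8 is a responder by design. Only the timing of the assessment is open to complaint.
- **The same bypass occurs at Week 28.** There is no general non-responder rule there to bypass. SAP 2.6.3 carries the last value forward when tapering success cannot be derived, and protocol 12.5.1 does so for missing body weight only. Non-response is imputed there only for intravenous steroid use.

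**Conclusion.** The point holds for the Week 8 primary endpoint. An EOS assessment on Days 32-56, up to 25 days early, counts as an available Week 8 value, so non-responder imputation is not applied. For participants who leave the trial at that visit, it also shortens the time in which a steroid increase could be seen.

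The size is 9.1 points per affected participant. That can decide the test only when the count is at the threshold: 8 of 11 for the uncorrected test, 9 of 11 for the corrected one. A flip from 7 to 8 should not be read as the planned test's behaviour, because the SAP leaves the correction open. Whether any of the 11 is affected is unknown from the documents.

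For Week 28 the finding is smaller: a value from up to 24 days early can carry the Week 28 label, and the two documents' carry-forward rules differ.

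**What to change.** For the Week 8 primary endpoint:
- Accept a mapped EOS value only within a stated tolerance of Day 57, for example Days 54-60, mirroring the table's own +3 days.
- Treat an earlier EOS visit with no named Week 8 visit as missing, under the existing non-responder rule. With Days 54-60 this concerns EOS visits on Days 32-53.
- Use a named Week 8 visit in preference to a mapped EOS visit; the SAP does not say which applies when both exist.
- Repeat the analysis with the wide window as a sensitivity analysis. The study is open-label and SAP 2.14 dates the data for the first 11 at 6 December 2022, so showing both results keeps the choice of window visible.

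Reconcile two further places. SAP 2.6.3 and protocol 12.5.1 should state one rule for underivable tapering status at Week 28 and how an early mapped EOS value enters it; SAP section 4 lists no change from the protocol. Protocol 9.1.1 should say whether participants who stop treatment leave the trial at EOS or return for follow-up visits.

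The cost is one rule in SAP 2.1.2 or Table 2-1, one extra table and two wording corrections. The downside is that the response rate may be lower, by 9.1 points for each early leaver whose EOS value was a response.
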